11.4 Slit Lamp Examination Outcomes

The number and percentage of subjects within each category of slit lamp examinations outcomes will be summarized by visit, by eye and by treatment. Shift from baseline will also be evaluated.

The categories for the Shift from baseline for 'Cornea', 'Conjunctiva', 'Iris', 'Lens' and 'Anterior Segment' assessments are defined as follow:

- Normal/clinically insignificant abnormality at Baseline to normal/clinically insignificant abnormality
- Normal/clinically insignificant abnormality at Baseline to clinically significant abnormality
- Clinically significant abnormality at Baseline to normal/clinically insignificant abnormality
- Clinically significant abnormality at Baseline to clinically significant abnormality

The categories for the Shift from baseline for 'Anterior chamber, hypopyon', 'Grading of anterior chamber cells', 'Grading of anterior chamber flare' and 'Vitreous inflammation quantification' assessments are defined as follow:

- Absent at Baseline to absent
- Absent at Baseline to present
- Present at Baseline to absent
- Present at Baseline to present

For 'Grading of anterior chamber cells' assessment, absent is defined as '0 Cells' and present is defined as any other category (except missing).

For 'Grading of anterior chamber flare' assessment, absent is defined as 'Complete absence' and present is defined as any other category (except missing).

For 'Vitreous inflammation quantification' assessment, absent is defined as '0' and present is defined as any other category (except missing).

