5.4 Benefit / Risk Assessment

No treatment currently exists for CHM.

The non-clinical studies conducted with AAV2-REP1 showed that it provides efficient and functional transgene expression in CHM mouse and human cells, as well as in mouse and human RPE and photoreceptors, without overt toxicity. Results from the 26-week single-dose combined toxicity/biodistribution study conducted in rats indicate that administration of AAV2-REP1 by single sub-retinal injection to both eyes is well tolerated at dose levels of 1×10^{9} and 6×10^{9} gp/eye (equal to 1×10^{11} and 6×10^{11} gp/eye in humans) when evaluated 4 and 26 weeks after injection. Minor reductions in some ERG parameters, ocular inflammation, and microscopic signs of retinal/corneal degeneration were observed and were considered procedure-related or not biologically significant.

In humans, application of AAV2-REP1 to the surface of the retina requires retinal detachment via vitrectomy. The 2-step procedure employed in delivering AAV2-REP1 subretinally (see Section 9.4), allows the management of unexpected surgical complications of retinal detachment before the AAV2-REP1 is applied. Furthermore, since the volume of fluid required to detach the fovea is variable, by excluding the vector from the first step, and administering the vector after successful retinal detachment has been achieved, a precise, consistent dose in terms of genome particles can be applied into the sub-retinal space. Sub-retinal injection of AAV2-REP1 does carry the risks associated with vitrectomy and retinal detachment, which include intra-operative and post-operative complications; infection (most notably infectious endophthalmitis); low and elevated IOP; choroidal detachment; persistent retinal detachment, retinal tears, holes and breaks; macular hole and macular oedema; vitreous haemorrhage; visual impairment; metamorphopsia; and photopsia (Park 1995; Thompson 1996; Banker1997; Cheng 2001; Anderson 2006; Stein 009; Recchia 2010). Post-operative intraocular inflammation caused by vitrectomy is often associated with transient and sometimes permanent visual impairment. Another complication of vitrectomy is cataract formation, which may require an additional surgical procedure (cataract extraction) (Park 1995; Cheng 2001; Recchia 2010). In addition, the surgical procedure is performed under general anesthesia, which includes the risks of dizziness, confusion, nausea and vomiting.

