12 ASSESSMENT OF SAFETY

12.1 Full Ophthalmic Examination

A full ophthalmic examination will be conducted for both eyes at the times indicated in Table 3.

For subjects in the AAV2-REP1 groups, the full ophthalmic examination will be conducted prior to pupil dilation and prior to vitrectomy and administration of study medication at the applicable study visit.

The ophthalmic examination will include IOP, slit lamp examination, lens opacity grading, and dilated ophthalmoscopy. The same slit lamp machine and lighting conditions should be used across study visits for any given subject.

In addition to the parameters listed above, relevant subjects will be carefully examined for the presence of intraocular inflammation after vector administration. Cataract can also develop as a result of the vitrectomy procedure and can potentially affect VA. Pre-operative grading of lens opacity and colour should therefore be documented by the established clinical lens opacities classification system. A recent study has shown that cataract surgery is effective in subjects with CHM and without any specific risks (Edwards 2015). Hence, if clinically indicated, subjects who develop cataracts may undergo cataract surgery. If cataract surgery is performed, it should be carried out at least 4 weeks before the Month 12 Visit/EOS Visit.

12.2 7-Field Colour Fundus Photography

To aid in the objective clinical assessment of progressive retinal changes, 7-field colour fundus photography will be performed for both eyes at the times indicated in Table 3.

Fundus photography will be performed by certified technicians following pupil dilation. Stereo photos should be performed for fields 1, 2, and 3. All fundus photographs will be sent by the sites to the CRC for review. For complete technical specifications for fundus photography, refer to the Study Operations Manual (which will include procedures from the CRC regarding how measurements are to be taken).

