5 GENERAL ASPECTS FOR STATISTICAL ANALYSIS

5.1 General Methods

All analyses and summaries will be produced using SAS® version 9.4 (or higher).

For descriptive summary statistics, the efficacy and safety data will be summarized and displayed by treatment groups (Control, Low Dose, High Dose) and visits (Baseline, Month 1, 4, 8, 12, and End of Study).

Summary statistics will be presented for continuous variables, by way of number of subjects, mean, standard deviation (SD), median, first and third quartiles (Q1 and Q3, respectively), 5th and 95th percentiles (P05 and P95, respectively), minimum and maximum. Where specified, the 95% Confidence Interval (CI) of the mean will be calculated. Summary statistics will be presented where appropriate by treatment and nominal visit with an additional entry for the end of study.

For categorical variables (including binary variables), counts and percentages will be presented. Where specified, the 95% 2-sided CI for proportions will be calculated.

The listings, except the listing for screen failures, will include all randomized subjects in the database. In general, the subject listings will be sorted by treatment group, subject number, eye (starting with the study eye) and assessment date (and time, if applicable).

Data for unscheduled assessments will be included when calculating baseline values, selecting worst result for shift analyses, and for summary of normal/abnormal values. The safety summary of observed and change from baseline data will be performed by nominal (i.e., scheduled) visits. Unscheduled visits will be included in the analysis of End of Study, i.e., the last available non-missing treatment endpoint.

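### The worst-result shift for anterior-chamber cells, flare and vitreous inflammation keeps only absent/present, and no planned table gives the worst post-baseline grade by arm

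*SAP*

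**What the plan says.** SAP 11.4 plans two displays of the slit-lamp findings.

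- **Category table.** "The number and percentage of subjects within each category of slit lamp examinations outcomes will be summarized by visit, by eye and by treatment". This keeps the recorded grades.
- **Shift from baseline.** Four items, including hypopyon, use an absent/present shift. For three of them a grade is collapsed to get there. Cells: "absent is defined as '0 Cells' and present is defined as any other category (except missing". Flare: "absent is defined as 'Complete absence' and present is defined as any other category (except missing". Vitreous inflammation: "absent is defined as '0' and present is defined as any other category (except missing".

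SAP 5.1 decides which visits feed which display. Unscheduled data are used for baseline, for "selecting worst result for shift analyses", and for normal/abnormal summaries. They also enter the End of Study entry, as the last available value. Otherwise, "The safety summary of observed and change from baseline data will be performed by nominal (i.e., scheduled) visits". The display visits named there are Baseline, Months 1, 4, 8 and 12, and End of Study. Day 1 and Day 7 are not named, although the schedule of procedures has a full ophthalmic examination on both days for treated subjects.

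Protocol 13.7.2 describes the slit-lamp shift as summarised by visit, treatment and eye, and does not mention a worst result.

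The protocol singles out inflammation. Section 12.1 says that "relevant subjects will be carefully examined for the presence of intraocular inflammation after vector administration", and section 5.4 says: "Post-operative intraocular inflammation caused by vitrectomy is often associated with transient and sometimes permanent visual impairment".

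**The concern.** An eye's peak inflammation is the figure a safety reader wants first, and it may well be seen at an unscheduled visit. The SAP sends worst and unscheduled results to the shift, and the shift for these three signs has no grade. A trace of cells after vitrectomy and a severe reaction both count as absent at baseline and present later.

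Controls have no surgery, so high dose against low dose is the randomised comparison in which both arms had the same procedure. If most operated eyes in both dose arms show some cells at some visit, a worst-result absent/present table will look alike in the two arms whatever the grades were. What is at stake is a clear descriptive picture of how severe inflammation became, by arm, for a sign that the protocol names for careful examination.

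**Working it through.** The plan states no figure for this point, so there is none to reproduce. The check is a comparison of sections, followed by an illustration.

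**1. Does any display show worst grade by arm?**

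| Display | Keeps the ocular grade? | Takes the worst result, with unscheduled visits? |
|---|---|---|
| SAP 11.4 category table | Yes, by eye and arm | No: nominal visits, plus the last value at End of Study |
| SAP 11.4 shift, cells/flare/vitreous inflammation | No | Yes under SAP 5.1; by visit under Protocol 13.7.2 |
| SAP 11.4 Anterior Segment and 11.6 Vitreous shifts | No: clinical significance yes/no | Yes under SAP 5.1 |
| SAP 11.1 TEAEs by maximum severity | No: AE scale | Any reported event |
| SAP 11.1 ocular-inflammation TEAEs, by onset up to or after 30 days | No | Any reported event |
| SAP 11.8 inflammation AEs against immunogenicity, by severity | No: AE scale | Any reported event |

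No row has the grade together with the worst result. The AE scale in Protocol 12.3.2 runs from easily tolerated to incapacitating. It grades effect on normal activity, not cells or flare.

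**2. Which peaks can the graded table miss?**

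- Any peak at an unscheduled visit, unless it is the last value. Protocol 10.10 requires the full ophthalmic examination at such visits, so the grade is recorded.
- Peaks at Day 1 and Day 7, if the visit list in SAP 5.1 governs 11.4.
- The schedule leaves room for unscheduled visits. Day 7 ± 3 ends at Day 10. Month 1 ± 7, taking a month as 30 days, starts at Day 23. The next examination is at Month 4.

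**3. How much detail does a comparable sign keep?** The lens opacity shift in SAP 11.5 splits worsening by starting category (1, 2 or 3). The inflammation shift has only one row for worsening.

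**4. Illustration (all rates assumed; the documents give none).** Planned arm sizes: 160 × 2/5 = 64 high dose and 160 × 1/5 = 32 low dose.

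Difference d = p_H − p_L, with Wald 95% CI d ± 1.96 × √[p_H(1 − p_H)/64 + p_L(1 − p_L)/32].

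- *Any present, about 90% in each arm:* 58/64 = 90.6% and 29/32 = 90.6%. d = 0, CI −12.4 to +12.4 points; Fisher p = 1.0. With exactly 70%, 90% or 98% in both arms d is still 0, with half-widths of 19.4, 12.7 and 5.9 points. The grades do not enter the result.
- *Worst grade at or above some cut, in the same eyes:*

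| High dose | Low dose | d (points) | 95% CI | Fisher p |
|---|---|---|---|---|
| 16/64 = 25.0% | 2/32 = 6.3% | 18.8 | 5.2 to 32.3 | 0.029 |
| 13/64 = 20.3% | 3/32 = 9.4% | 10.9 | −3.2 to 25.0 | 0.25 |
| 10/64 = 15.6% | 2/32 = 6.3% | 9.4 | −2.9 to 21.6 | 0.33 |

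The Wald intervals are rough with so few low-dose events. SAP section 11 plans no inferential safety analysis, so the p-values only give scale.

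**The case against.** A reader might infer that the dose arms cannot be told apart on inflammation. The documents do not support that. The category table in SAP 11.4 counts every grade by visit, eye and treatment, and SAP 11.1 and 11.8 tabulate AE severity and inflammation events by arm.

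A reader might also infer that the dose contrast is the plan's only means of separating vector from surgical inflammation. That is too strong as well. SAP 11.1 splits inflammation events by onset, and SAP 11.8 relates them to antibody and T-cell results. Protocol 9.8 gives steroids for surgical inflammation as well as for immune responses, and the protocol's change summary says the low dose was added to support masking.

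The argument that absent/present sits near its ceiling depends on reading SAP 5.1 as a worst-value shift. SAP 11.4 does not say so, and Protocol 13.7.2 says by visit. On the by-visit reading, Protocol 9.6.1 expects signs of surgery to be gone by Month 1, so a finding that is present from then on would be informative. The Anterior Segment and Vitreous shifts also separate minor from clinically significant abnormality.

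These points limit the concern but do not remove it. On either reading the shift for the three signs has no grade. The clinical-significance shifts are two-level judgements, not inflammation grades. None of the other tables gives an eye's worst grade.

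**Conclusion.** The point holds in a limited form. For cells, flare and vitreous inflammation, the only display that takes the worst result including unscheduled visits discards the grade, and no visible table gives worst post-baseline grade by arm. Comparison of the dose arms by grade remains possible at the scheduled visits shown. What can be lost is the height of a peak at an unscheduled visit, and at Day 1 or Day 7 if the visit list in SAP 5.1 applies to 11.4.

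The size cannot be stated from the documents. In the illustration, absent/present shows 0 points while a worst-grade cut shows about 9 to 19 points. The 90% and the 25% v 6% are assumptions, and other counts give other answers. The conclusion also assumes that SAP 5.1 governs the shift; if Protocol 13.7.2 governs, no slit-lamp display of these three signs uses the worst result at all. This is a descriptive improvement at almost no cost and does not touch the efficacy analysis.

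**What to change.** In SAP 11.4:

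1. For cells, flare and vitreous inflammation, replace the absent/present shift by a table of baseline grade against worst post-baseline grade, by eye and arm, using the grades already recorded.
2. Include Day 1, Day 7 and unscheduled visits. Show the worst grade up to the Month 1 visit and the worst grade after it separately.
3. Keep absent/present for hypopyon.
4. State whether Day 1 and Day 7 appear in the by-visit category table.
5. Reconcile Protocol 13.7.2 (shift by visit) with SAP 5.1 (worst result), and say in 11.4 which applies.
6. Label the table descriptive, without tests. Controls are contacted by telephone on Days 0, 1 and 7, so a footnote should say that they have no scheduled eye examination before Month 1.

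The cost is one changed table shell and a few sentences. No new data are needed.

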11.5 Lens Opacity Grades

The number and percentage of subjects within each category of nuclear opalescence grade, nuclear colour grade, cortical cataract grade and posterior cataract grade will be summarized by visit, by eye and by treatment. Shift from baseline will also be evaluated.

The categories for lens opacity grades are defined as Category 1, 2, 3 and 4.

The categories for the Shift from baseline are defined as follow:

- No change in category
- Decrease in category
- Category 1 at Baseline to Category 2, 3 or 4
- Category 2 at Baseline to Category 3 or 4
- Category 3 at Baseline to Category 4

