These treated subjects will then return to the site for 2 post-operative follow up visits on Day 1 (Visit 3) and, possibly, Day 7 (Visit 4; Day 7 can occur either at the surgical site or the host site, depending on the clinical status of the subject). Subjects in the Control group will not undergo surgery, receive study drug or attend the 2 on-site safety post-operative visits.

Instead, a telephone contact from the site will occur for the Control group on Day 0 (Visit 2), Day 1 (Visit 3) and Day 7 (\pm 3 days; Visit 4).

All subjects will be followed for 12 months from Visit 2 (Day 0). Study data will be collected for both eyes of each subject.

Since AAV2-REP1 treatment requires an invasive surgical procedure under general anaesthesia, the sponsor, investigator and the subject will be unmasked to the study procedure (i.e. vitrectomy and sub-retinal injection), however within the treated groups, the sponsor, investigator and subject will be masked to the assigned dose $(1.0 \times 10^{11} \text{ gp or } 1.0 \times 10^{10} \text{ gp})$. To further minimise the potential bias of the treated and untreated eye evaluations, all subjective ophthalmic assessments from the Screening/Baseline period (Visit 1) and from Month 1 (Visit 5) onwards, will be conducted by a masked assessor. Subjects will be assessed for efficacy and safety throughout the study as indicated in the Schedule of Study Procedures (see Section 17.1).

The efficacy evaluation will be based on BCVA, fundus AF, SD-OCT, microperimetry, contrast sensitivity, colour vision, reading speed test, VFQ-25

. The safety evaluation will be based on full ophthalmic examination (including IOP, slit lamp examination, lens opacity grading, and dilated ophthalmoscopy), fundus photography, adverse event (AE) reporting, laboratory assessments (immunogenicity), and vital signs. Any safety information collected as a result of the efficacy assessments (e.g., BCVA) will also be used in the overall safety evaluation, as appropriate.

Subjects who develop cataracts may undergo cataract surgery if deemed clinically necessary; if surgery is performed, it should be carried out at least 4 weeks before the Month 12 Visit/End of Study (EOS) Visit (primary endpoint).

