13.7.2 Full Ophthalmic Examination

Intraocular pressure and change from Baseline in IOP will be summarised by visit, by treatment and by eye. Abnormal slit lamp examination findings and dilated ophthalmoscopy findings, and shift from Baseline will be summarised by visit, by treatment and by eye.

Lens opacity categories and shift from Baseline will be summarised by visit, by treatment and by eye.

13.7.3 7-Field Colour Fundus Photography

Categories of colour fundus photography findings and shift from Baseline will also be summarised by visit, by treatment and by eye.

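### The SAP's lens-opacity tables have no state for a removed lens, so eyes that undergo cataract extraction would drop out of them, probably understating lens worsening in the vitrectomised arms

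*SAP*

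**What the plan says.** SAP 11.5 covers four lens scales: nuclear opalescence, nuclear colour, cortical cataract and posterior cataract. For all of them, "The categories for lens opacity grades are defined as Category 1, 2, 3 and 4". Results are shown by visit, eye and treatment. The shift rows are no change, "Decrease in category", and increases starting from Category 1, 2 or 3. Nothing is said about a lens that is absent or artificial.

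Protocol 13.7.2 sets the layout: "Lens opacity categories and shift from Baseline will be summarised by visit, by treatment and by eye". SAP 5.1 has a general rule that unscheduled data are used when "selecting worst result for shift analyses". SAP 11.5 does not say which of these governs its shift table. Protocol 13.2 adds that safety data are analysed as observed and not imputed.

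On cataract itself, Protocol 5.4 says: "Another complication of vitrectomy is cataract formation, which may require an additional surgical procedure (cataract extraction"). Protocol 7.1 provides that "Subjects who develop cataracts may undergo cataract surgery if deemed clinically necessary", and Protocol 12.1 repeats the permission: "if clinically indicated, subjects who develop cataracts may undergo cataract surgery". On the comparator, Protocol 7.1 says: "Subjects in the Control group will not undergo surgery, receive study drug or attend the 2 on-site safety post-operative visits".

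**The concern.** Lens grading is the plan's graded, between-arm look at a complication that the protocol expects from the study procedure. The eyes with the worst lens outcome are those whose cataract is extracted, and these are the eyes the table cannot hold once the lens is out. Because only the treated arms have vitrectomy, the loss should fall mainly on them. That is informative exclusion in a safety comparison: the more extractions there are, the more the treated arms' remaining graded eyes are those that did comparatively well.

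No other planned table shows extractions directly. Protocol 9.8 requires concomitant procedures to be recorded, but SAP 9.3 describes tables for medications only.

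**Working it through.** The documents give no cataract figure to reproduce, so the check has three parts.

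**1. Do the rows cover every state?** Four grades at Baseline by four at follow-up give 4 × 4 = 16 cells. The five rows cover all 16: 4 no change, 6 decrease, 6 increase (3 from Category 1, 2 from Category 2, 1 from Category 3). Adding a lens-removed state gives 5 × 5 = 25 cells, so 25 − 16 = 9 have no row:
- 4 are a graded lens at Baseline removed on study;
- 1 is a lens already removed at Baseline;
- 4 are impossible (removed, then graded).

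Five feasible states therefore have no place in the table.

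**2. Can those states occur, and where?**
- *Removal on study* is expected and permitted (Protocol 5.4, 7.1, 12.1). Clinically significant cataract is excluded at entry (Protocol 8.2), so extractions would mostly follow worsening on study. Protocol 7.1 places any cataract surgery at least 4 weeks before Month 12, so an eye extracted on that schedule reaches the Month 12 table without its natural lens.
- *Removal before Baseline* is possible because Protocol 8.2 excludes earlier intraocular surgery in the study eye only within 3 months of Visit 1.
- *Handling*: with observed-data analysis (Protocol 13.2), an ungraded eye leaves the by-visit numerator and denominator. If SAP 5.1's End of Study entry (last non-missing value) is used, it would show a grade from before the extraction.

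**3. What size could it have?** This is illustration only, and every rate is assumed. Take 96 treated study eyes (64 + 32, SAP 3.6). Let w = 29 (about 30%) worsen with the lens in place, and let x eyes be extracted after worsening, at about 5%, 10% or 20%.

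- With extractions counted once as an unfavourable outcome: (w + x)/96
- With extracted eyes dropped: w/(96 − x)

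| x | (29 + x)/96 | 29/(96 − x) | Shortfall, points |
|---|---|---|---|
| 5 | 34/96 = 35.4% | 29/91 = 31.9% | 3.5 |
| 10 | 39/96 = 40.6% | 29/86 = 33.7% | 6.9 |
| 19 | 48/96 = 50.0% | 29/77 = 37.7% | 12.3 |

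If extracted eyes were instead given a low grade, worsening would read 29/96 = 30.2% in every row. These percentages describe a single any-worsening measure. SAP 11.5 plans four separate scales, so no planned table would print them. They show direction and rough scale only.

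**The case against.** The strongest reply is that cataract harm is not lost. Protocol 12.3.2 has all adverse events recorded whatever their cause, and SAP 11.1 tabulates treatment-emergent events by preferred term and treatment, with ocular events by eye, and also by severity, relatedness and seriousness. A cataract bad enough to extract belongs there, and extraction does not erase it. This stands, and it confines the point to SAP 11.5.

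Second, if SAP 5.1's worst-result rule governs the shift table, an eye graded worse before extraction keeps that grade there. Clinically indicated unscheduled visits must include lens grading (Protocol 10.10), which improves the chance of catching it. This stands in part. Protocol 13.7.2 asks for shift by visit, SAP 11.5 does not settle the matter, and the by-visit grade tables lose the eye under either rule.

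Third, a reader might infer that extracted eyes will look improved. The documents do not support that. They give no coding rule for a removed lens, and a "Decrease in category" needs both an artificially low grade and a Baseline grade above Category 1.

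Fourth, counting removal as progression on every scale would err the other way: an eye extracted for posterior cataract would also register as worse in cortical grade, opalescence and colour. This is right, and it shapes the fix.

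A reader might also extend the point to the 'Lens' rows of SAP 11.4. Those rows separate normal or clinically insignificant findings from clinically significant ones, and can take any examined eye, so no defect is shown there.

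**Conclusion.** The gap is real. The closed set of categories, combined with observed-data analysis, leaves an extracted eye either out of the by-visit lens-opacity tables or in a grade that does not describe it. Lens worsening in the vitrectomised arms is then likely to be understated.

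The direction rests on two assumptions that the protocol makes reasonable: extractions occur mainly in treated eyes, and they mostly follow worsening on study. The size is unknown, and the figures above depend wholly on assumed rates.

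The documents do not support a broader claim that the trial's cataract safety reporting as a whole is biased. Safety analyses are descriptive (Protocol 13.7), and type I error, power and the primary test are unaffected. The change should still be made, because the tables compare arms on an expected complication and the remedy uses data already collected.

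**What to change.** In SAP 11.5:
- Add a post-baseline row, 'lens removed since Baseline (pseudophakic/aphakic)', and keep those eyes in the denominator.
- Show eyes already without a natural lens at Baseline separately.
- Present removal as its own unfavourable outcome, or within one summary of any worsening or extraction for cataract. Do not count it as progression on each of the four scales.
- State whether the shift is by visit (Protocol 13.7.2) or worst post-baseline (SAP 5.1).

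Also tabulate cumulative cataract extractions by arm and eye from the recorded concomitant procedures. No change to SAP 11.4 is needed on this evidence.

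The cost is one derived flag, one extra table and a possibly less favourable figure. No clinical procedure or data collection changes.
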